## **Data Collection Period**

Prospective patient identification will be undertaken over a three-month period – 31st October 2019 to January 31st 2020. Patients will then be followed by for 90 days – 30th April 2020. For one-year follow-up, NELA and ELLSA databases (already collecting such data) will be accessed and both have already provided provisional approvals.

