## Aims

This study aims to:

1) Identify a U.K. consecutive series of older adults presenting with acute abdominal pathology potentially treatable by emergency laparotomy where the decision is made not to undergo surgery (NoLAP) and their associated 90-day mortality.

2) Collect, define and characterise the reasoning behind the NOLAP decision.

3) Define potential prognostic markers for mortality that could aid decision-making in the future (including frailty, NELA score and sarcopenia).

4) Compare aims 1 and 3 to those that underwent surgery (ELAP) during the same time frame as the NoLAP population.

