#### Method

#### Ethics

Ethical approval will be obtained from IRAS. As per ELF, this will involve a proportionate ethical review given that this is merely an observational study and not altering patient care. Permission with be sought by the study team from the Caldicott Guardian for entry of pseudoanonymised data into REDCap (Scotland: Public Benefir and Privacy Panel for Health and Social Care, PBPP; England and Wales: Confidentiality Advisory Group).

No data will be entered from any site that has not provided such written evidence (electronically or paper). In addition, each site will be individually responsible for ensuring that all members of their team have an up to date Good Clinical Practice (GCP). REDCap will be provided and maintained by the Swansea Clinical Trials Unit.

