#### Variables collected

The following clinical parameters will be collected for NOLAP population: age; sex; place of residence (home with no carers, home with carers, intermediate care, residential home, nursing home); ASA (American Society of Anaesthesiologists); surgical diagnosis (pre-operatively); NELA score; Clinical Frailty Score (Rockwood, 1 to 7); co-morbidities (Charlson; total number of co-morbidities); polypharmacy (5+ medications: yes/no) CT performed within 48 hours of decision (yes/ no); CT

diagnosis; date of assessment for laparotomy, time of day and location (most relevant according to the following list: general surgical ward; other surgical ward; orthopaedics; gynaecology; geriatrics; acute medical ward; other medical ward). Preoperative (within 8 hours of surgical decision) blood markers will also be recorded: lactate; C reactive protein; creatinine and WCC. The actual procedure performed will be recorded for the ELAP patients only.

For comparison to ELAP. This data will be retrieved directly from NELA and ELLSA databases with no extra data required by each participating site.

Remaining variables: length of hospital stay; length of critical care stay (ICU and HDU combined). Both groups will then be followed up for: 30-day complications (Clavien-Dindo Grading); date of discharge; discharge destination (home with no carers, home with carers, intermediate care; residential home, nursing home); 30-day and 90-day mortality and death at 1 year. Actual date of death and cause of death (1a on death certificate) will be recorded.

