# June 1st 2019 31st July 2019 Finalising of protocol th c c+

## **DtD Study Timeline**

IRAS and REDcap set up	June 1 st 2019	30 th September 2019
Drafting of protocol paper	June 1 st 2019	31 st December 2019
Funding Applications	July 1 st 2019	January 31 st 2020
Advertising for sites	July 4 th 2019	31 st October 2019
Site registration	July 4th 2019	31 st October 2019
Local Approvals	July 4 th 2019	30 th November 2019
REDcap data upload	31 st October 2019	January 31 st 2020
Follow-up data uploaded	January 31 st 2020	30 th April 2020
1 st Data completion	31 st May 2020	
1 st Data analysis	30 th April 2020	31 st July 2020
1 st write up completed	1 st September 2020	
Dissemination	1 st September 2020	1 st December 2020
2 nd data completion	30 th April 2021	
2 nd Data analysis	30 th April 2021	31 st July 2021
2 nd write up completed	1 st September 2021	
Dissemination and End of study	1st November 2021	

Shading indicates the one year follow-up period.

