## Data Input Procedure

Data collection will be using the secure REDcap system. All data will be handled in accordance with the Data Protection Act 1998 and GDPR 2018. Each local lead will be provided with a unique username and password and collected prospectively for maximum accuracy. Completed datasheets will be entered into the secure REDcap system REDcap will be hosted by the University of Swansea.

REDcap accounts will not be issued until evidence is provided via hospital local leads that the following approvals are in place at each centre:

- i. Successful registration of ELF at the hospital site
- ii. Caldicott Guardian permission for data to be submitted to REDcap

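### ELAPs are not tied to each site's own NoLAP capture dates, so late site approval can bias the primary NoLAP proportion low

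*Protocol*

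**What the plan says.** Protocol, Data Collection Period: "Prospective patient identification will be undertaken over a three-month period", given as 31 October 2019 to 31 January 2020.

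Protocol, DtD Study Timeline: the row "Local Approvals" runs from 4 July to 30 November 2019. Site registration stays open until 31 October 2019, the day identification starts.

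Protocol, Ethics: "No data will be entered from any site that has not provided such written evidence". Data Input Procedure adds: "REDcap accounts will not be issued until evidence is provided via hospital local leads that the following approvals are in place at each centre".

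Protocol, Identification of the NOLAP: sites find NoLAP patients by active local work, with daily contact with the on-call team and review of the CT list encouraged.

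Protocol, Variables collected, on the ELAP comparators: "This data will be retrieved directly from NELA and ELLSA databases with no extra data required by each participating site".

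Protocol, Aims, aim 4: the comparison is with patients who had surgery "during the same time frame as the NoLAP population".

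Protocol, Data analysis: the NoLAP proportion is named as a primary outcome, to be reported with a 95% confidence interval. Patient numbers and power calculation sizes the study on that proportion.

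**The concern.** A proportion of NoLAPs among all patients needing emergency laparotomy requires numerator and denominator from the same hospitals over the same days. Here they come from two systems that start differently. NoLAPs depend on a study team working at the site and on permission to enter data. ELAPs sit in audits that run regardless of the study. If a site begins capturing NoLAPs late and its ELAPs are still drawn for the full three months, the denominator covers days that the numerator does not, and the share comes out too low. Part of the variation between hospitals would then reflect approval dates.

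A larger sample would not remove this bias, and the confidence interval would not reveal it. Nor could it readily be repaired at analysis, because the dates needed are not collected. The site profile (Profile of Centre) lists no opening or closing date. Variables collected mentions a date of assessment, but the proforma (Appendix B, Q16 and Q17) records only a weekday band and a clock time.

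**Working it through.** **The plan's own figure.** With p = 0.32 and half-width d = 0.0375, n = 1.96² × 0.32 × 0.68 / 0.0375² = 594.4. The stated 590 gives a half-width of 3.76 points, so the planned precision is reproduced. It serves below as the yardstick for the bias.

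**Inputs from the Protocol**
- Window: 31 October to 31 January inclusive = 1 + 30 + 31 + 31 = 93 days.
- Latest local approval: 30 November, 30 days after the window opens, leaving 63 of 93 days (68%).
- Expected NoLAP share: p = 32%.

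**Assumptions, not in the Protocol**
- ELAPs are counted over all 93 days at every site.
- A late site contributes no NoLAPs from before it opened.
- Cases arise evenly over time, with the same true share at every site.
- The fraction f of site volume that opens late, and the delay in days, are unknown and are varied.

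The proforma carries some items that apply only to ELAP patients. Because Variables collected says sites supply nothing extra for that group, the audits are taken as the source.

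**Formula.** The fraction of NoLAPs captured is c = 1 − f × delay / 93. The expected estimate is p·c / (p·c + 1 − p).

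For f = 0.5 and a 30-day delay: c = 1 − 15/93 = 0.839, and 0.2684 / (0.2684 + 0.68) = 28.3%.

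| Site volume opening 30 days late | c | Expected estimate | Shortfall (points) |
|---|---|---|---|
| 10% | 0.968 | 31.3% | 0.7 |
| 25% | 0.919 | 30.2% | 1.8 |
| 50% | 0.839 | 28.3% | 3.7 |
| 100% | 0.677 | 24.2% | 7.8 |

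Half the volume opening 15 days late gives the same 30.2% as a quarter opening 30 days late, because only the mean delay matters.

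**Delay at which the bias equals the planned half-width.** Setting the estimate to 32 − 3.75 = 28.25% gives c = 0.2825 × 0.68 / (0.32 × 0.7175) = 0.837, a mean delay of 93 × (1 − 0.837) = about 15 days across site volume.

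**At a lower true share.** The Background also cites an Australian audit with a 6% NoLAP share. At p = 0.06, the estimate is 5.1% if half the volume opens 30 days late and 4.1% if all does.

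**After matching dates.** If a late site's ELAPs are cut to the same 63 days, the share is 0.32 × 63 / (0.32 × 63 + 0.68 × 63) = 32.0%, and the bias is gone.

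**The case against.** The strongest reply is that the Protocol restricts data entry, not identification. Data Input Procedure describes datasheets being completed and then entered, so a site could note cases from 31 October and enter them once approved. Full back-entry would remove the bias. This stands, and it is why the point is conditional. The Protocol does not provide for that route, however, and describes identification and collection as prospective. Partial back-entry would still leave the share low.

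A second reply is that aim 4 already asks for the same time frame, and that filtering an extract by date belongs in the SAP. Aim 4 could be applied site by site, but it speaks of the NoLAP population as a whole, and the natural frame is then the single three-month window. A SAP can filter only on dates that have been collected.

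A third reply is that approvals open on 4 July 2019, about 17 weeks before identification, so few sites may be late. That is fair. The Protocol gives neither the number of late sites nor their delays, and at 10% of volume the loss is only 0.7 points.

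A reader might infer three further faults that the Protocol does not support:
- **Closing early at 700.** The window is set by calendar dates. The 700 is a sample-size target, and no stopping rule is attached to it.
- **Losing late-January cases because upload ends on 31 January.** Follow-up upload runs to 30 April and first data completion is 31 May. Nothing shows that such cases would be dropped.
- **Bias in the mortality comparison.** Extra ELAP days at the same hospitals add comparators. No distortion of 90-day mortality follows from that alone.

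**Conclusion.** The point holds as a conditional bias in the NoLAP proportion. The approval dates, the bar on data entry and the separate source of ELAPs are all in the Protocol, and nothing in it aligns the two counts site by site or collects the dates needed to do so. If late sites do not fully back-enter and ELAPs are taken over the whole window, the proportion is biased low.

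The size depends on lateness that the Protocol does not state: 0.7 points at 10% of volume, 1.8 at a quarter and 3.7 at half. The 7.8 points if all volume opens 30 days late is an upper bound, not a forecast. It would be too strong to say that the plan as written must understate the proportion.

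One related error runs the other way. Profile of Centre records whether a site takes part in NELA or ELLSA but does not make it a condition. A site contributing NoLAPs with no audit ELAPs would push the share up.

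**What to change.** - Record for each site the dates on which NoLAP capture opened and closed. If a site back-enters all cases from 31 October, that date is its opening date.
- Record the calendar date of each NoLAP decision on the proforma, in line with the assessment date already listed in Variables collected.
- For the NoLAP proportion, count each hospital's ELAPs aged 65 or over only between its own capture dates. The audit extract must carry a date that allows this.
- Count only sites with audit data in the proportion.
- State these rules in aim 4 and in Variables collected.

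The cost is two date fields per site, one date per NoLAP patient, a date filter on the audit extract, and slightly fewer ELAPs.

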# June 1st 2019 31st July 2019 Finalising of protocol th c c+

## **DtD Study Timeline**

IRAS and REDcap set up	June 1 st 2019	30 th September 2019
Drafting of protocol paper	June 1 st 2019	31 st December 2019
Funding Applications	July 1 st 2019	January 31 st 2020
Advertising for sites	July 4 th 2019	31 st October 2019
Site registration	July 4th 2019	31 st October 2019
Local Approvals	July 4 th 2019	30 th November 2019
REDcap data upload	31 st October 2019	January 31 st 2020
Follow-up data uploaded	January 31 st 2020	30 th April 2020
1 st Data completion	31 st May 2020	
1 st Data analysis	30 th April 2020	31 st July 2020
1 st write up completed	1 st September 2020	
Dissemination	1 st September 2020	1 st December 2020
2 nd data completion	30 th April 2021	
2 nd Data analysis	30 th April 2021	31 st July 2021
2 nd write up completed	1 st September 2021	
Dissemination and End of study	1st November 2021	

Shading indicates the one year follow-up period.

## Patient numbers and power calculation

ELF Study recruited 957 patients from 49 sites and had a mortality of 20% at 90-days, similar to NELA findings (17-25% with increasing age). For aim 1: From previous work it is estimated that the proportion of patients to experience an NoLAP is approximately 32%. We will estimate this proportion with a 95% within +/- 3.75% by following up 590 patients, and assuming a small loss to follow up rate of 10%, we will recruit 700 patients.

With 25 000 ELAPs recorded every year in England and Wales, 32% of NoLAPs gives an estimate of 8000 NOLAPS per year. For a 3-month recruitment window we predict that the recruitment pool is 2000 making the study target of 700 achievable.

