# STUDY SYNOPSIS

Title of Study:	Defining the Denominator: Emergency Laparotomy and Frailty Study 2.	
Study Centre:	Multicentre	
Duration of Study:	25 months	
Primary Objective:	Identify a U.K. consecutive series of older adults presenting with acute abdominal pathology potentially treatable by emergency laparotomy where the decision is made not to undergo surgery (NoLAP) and their associated 90- day mortality.	
Secondary Objective:	Collect, define and characterise the reasoning behind the NOLAP decision.	
Primary Endpoint:	Characterise NoLAP patient populations and document 90-day mortality.	
Rationale:	Older patients that require, but do not undergo emergency laparotomy (NoLAP) are an undefined and uncharacterised population. In contrast to those older adults that undergo emergency surgery, it is not known how many patients constitute this NoLAP group, what characteristics they have, what the reasons are for not undergoing surgery and what their short-term outcomes are.	
Methodology:	Prospective cohort study	
Sample Size:	700	
Screening:	n/a	
Registration/ Randomisation:	Via REDCap database.	
Main Inclusion Criteria:	
 
65 years or older
 
requires emergency laparotomy for pathology consistent with inclusion into NELA
 
does not undergo emergency laparotomy
 
had review by trained surgeon
 
	
Main Exclusion Criteria:	
 
under 65 years of age
 
no surgical review
 
failed conservative management
 
	
Product, Dose, Modes of Administration:	N/A	
Duration of Treatment:	N/A	
Statistical Analysis:	Detailed later.	

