There are only two published works that have reported on the NoLap population. The Perth (Australia) Emergency Laparotomy Audit prospectively collected NoLAP numbers as part of analysing ELAP patients and found them to account for only 6% of the overall population being considered for emergency laparotomy [7]. However, this small number limits characterisation of NoLAP patients and more importantly, comparison to ELAP patients. The second study prospectively recorded over three hundred patients requiring ELAP for over 14 months [8]. Patients were included according to the NELA criteria with both groups having the same data recorded. In addition, the casenotes were reviewed to ascertain the reason for the NoLAP decision. This study found NoLAPs accounted for a third of all patients (32%) requiring an ELAP with a third of these being alive at 30 days with normal admission creatinine and lactate levels increasing the likelihood of survival. This is the first work that has attempted to characterise the U.K. NoLAP population, but is limited by being both single centred and by providing limited information on the decision behind NoLAP.

We aim to apply the findings and challenges from this work into the design of this multi-centred cohort study, to definitively define the denominator.

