## Outcomes

**Primary Outcome** Characterise NoLAP patient populations and document 90-day mortality.

Secondary Outcomes: Reasons for decision not to operate.

Prognostic scores: NELA score; Clinical Frailty Score.

Surgical diagnosis

Blood markers pre-operatively: lactate; C reactive protein; creatinine and WCC.

Length of critical care stay (ICU and HDU combined).

Length of hospital stay.

30-day complications

Discharge destination

30-day and 90-day mortality

Death at 1 year.

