## Data analysis

Statistical support will be provided by the study statistician ([name]) throughout the project.

Description of demographics of included patients including their demographics (gender, age), baseline clinical characteristics (frailty score, NELA score, comorbidities and polypharmacy). Complications and outcomes (Clavien-Dindo, discharge destination, 30 and 90-day mortality) will also be described. Missing/incomplete data will be presented and explored.

The Primary outcome to estimate the NoLAP proportion will be carried out with an asymptotic method, and presented with a 95% confidence interval.

The primary outcome to estimate the difference in 90-Day mortality between those with a NOLAP and ELAP will be carried out with a multi-level logistic regression, fitting patients within hospitals as a random site effects. The model will be adjusted for pre-operative patient: age; sex; and frailty status.

A full Statistical analysis plan will be reported prior to the data lock, and will be largely described in the published protocol.

Following analysis, each unit will be offered to receive their own raw data, and a summary of national data. This will allow comparison to local performance and enable local quality improvement work.

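### The sample-size calculation sizes the NoLAP share of all patients needing laparotomy, but its result of 700 is then used as a count of NoLAP patients, and the step from 590 to 700 is not a 10% inflation

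*Protocol*

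**What the plan says.** The Protocol's section on patient numbers and power calculation sizes aim 1. It says that "it is estimated that the proportion of patients to experience an NoLAP is approximately 32"%, and continues: "We will estimate this proportion with a 95% within +/- 3.75"%, to be achieved "by following up 590 patients, and assuming a small loss to follow up rate of 10%, we will recruit 700 patients". The Background section gives the source of the 32%: in a single-centre UK study, "NoLAPs accounted for a third of all patients (32%) requiring an ELAP". The base is therefore everyone who needed the operation, whether or not it was done.

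The next paragraph of the sample-size section takes 25,000 ELAPs a year, derives 8,000 NoLAPs a year, and concludes that for a three-month window "we predict that the recruitment pool is 2000 making the study target of 700 achievable". The Study Synopsis gives a sample size of 700 beside a main inclusion criterion that the patient "does not undergo emergency laparotomy". Under Variables collected, ELAP data come from the two national audit databases, with no additional collection by sites.

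On what is primary, the Synopsis and the Outcomes section agree: "Characterise NoLAP patient populations and document 90-day mortality". The Data analysis section differs. It states that "The Primary outcome to estimate the NoLAP proportion will be carried out with an asymptotic method", and then also labels as primary the adjusted difference in 90-day mortality between NoLAP and ELAP patients.

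**The concern.** A sample made up only of NoLAP patients cannot estimate the share of patients who are NoLAP, because that needs the ELAP patients in the denominator. The sizing paragraph and the feasibility paragraph therefore count different populations under the same number.

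Three things follow.

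- A reader cannot tell from the text which count of 700 would show that the target was met. The two readings differ about three-fold in NoLAP patients.
- The only precision the protocol states does not apply to NoLAP 90-day mortality, which two sections name as the primary endpoint.
- The 10% allowance is attached to the wrong quantity and does not give 700. Loss to follow-up affects 90-day mortality. It does not affect whether a patient was NoLAP or ELAP, which is known at the decision.

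**Working it through.** **Inputs.** Sample-size section: p = 0.32, half-width d = 0.0375, 95% confidence, 590 followed, 10% loss, 700 recruited, 25,000 ELAPs a year, 8,000 NoLAPs a year, pool 2,000. Background: the 32% is a share of all patients requiring the operation; about a third of NoLAP patients were alive at 30 days. The protocol gives no NoLAP 90-day mortality, so 20% to 80% is assumed here. The value 67% (one minus a third) is a 30-day, single-centre figure and serves only as a reference point.

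**Step 1: the plan's 590.** n = 1.96² × p(1 − p)/d² = 1.96² × 0.32 × 0.68/0.0375² = 594. With n = 590 the half-width is 1.96 × √(0.32 × 0.68/590) = 3.76 points. So 590 reproduces, as a total of NoLAP and ELAP patients.

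**Step 2: 590 to 700.** 590/(1 − 0.10) = 656; the cruder 590 × 1.10 = 649. Neither is 700. In reverse, 1 − 590/700 = 15.7% loss, and 10% loss from 700 leaves 630. A continuity-corrected calculation would need 621, and 621/0.9 = 690, close to 700, but the protocol starts from 590.

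**Step 3: what 700 counts.** The pool is 25,000 × 0.32 = 8,000 NoLAPs a year, and 8,000/4 = 2,000 in three months. So 700 is compared with NoLAP patients only, as in the synopsis.

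**Step 4: precision for NoLAP 90-day mortality**, with half-width 1.96 × √(m(1 − m)/n) and 10% loss in both readings:

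| Reading of 700 | NoLAP patients | Followed | m = 20% or 80% | m = 67% | m = 50% |
|---|---|---|---|---|---|
| NoLAP patients | 700 | 630 | 3.1 | 3.7 | 3.9 |
| NoLAP + ELAP | 0.32 × 700 = 224 | 202 | 5.5 | 6.5 | 6.9 |

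Half-widths are in percentage points and ignore clustering by hospital. A design effect D would multiply each by √D; the protocol gives no value from which to compute D.

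**Step 5: the denominator for the NoLAP share if 700 are NoLAP patients.** The protocol uses 32% in two ways.

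- As a share of all patients (Background): 700/0.32 = 2,188 in total, half-width 1.96 × √(0.32 × 0.68/2,188) = 1.95 points.
- On the feasibility ratio of 8,000 NoLAPs to 25,000 ELAPs: 700 × 25,000/8,000 = 2,188 ELAPs, so about 2,888 in total. The share is then 8,000/33,000 = 24.2%, not 32%.

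Applying the Background definition to the pool gives 25,000 × 0.32/0.68 = 11,765 NoLAPs a year, or 2,941 in three months. The stated pool of 2,000 is therefore conservative.

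**The case against.** The strongest reply is that little depends on the slip. Every operational use of 700 points to NoLAP patients: the inclusion criteria, the pool, and the ELAP data drawn from audits. On that reading, 630 followed patients give a mortality half-width close to the 3.75 points stated, and 700 exceeds the 656 that a correct inflation requires. This stands, and it limits the damage. It does not make the stated calculation a justification for that number.

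A reader might go further than the protocol supports in four ways.

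- **That sites would not know when to stop recruiting.** The Data Collection Period section fixes a three-month window for a consecutive series, with no stop at a count. The number is a planning target.
- **That 3.75 points describes no primary outcome.** With 590 as the total, it does describe the NoLAP share, which the Data analysis section calls primary. The fault is that this section disagrees with the Synopsis and Outcomes sections.
- **That the study is too small.** This would follow only if 700 were the combined total, which the operational text does not suggest.
- **That 3.9 points is the worst case.** It is the largest value under simple random sampling. The Data analysis section itself fits hospital as a random effect, so the real interval may be wider.

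The protocol defers a full statistical analysis plan, which may settle the analysis. That would not reconcile the calculation, target and primary outcomes that the protocol itself states.

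**Conclusion.** The point holds as an error of justification and labelling. The sample-size text sizes the NoLAP share with a denominator of about 590 to 595 patients of both kinds, then uses 700 as a count of NoLAP patients. NoLAP 90-day mortality has no stated precision. Three different quantities are called primary in different sections.

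The inflation is miscalculated by 44 patients (700 against 656) in the safe direction, and 700 may simply have been rounded up. The text nonetheless presents it as the result of 10% loss.

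If 700 counts NoLAP patients, as most of the text indicates, precision for the mortality endpoint is about 3.1 to 3.9 points and the design is adequate for estimation. If it is the combined total, precision is about 5.5 to 6.9 points. Both ranges assume mortality between 20% and 80%, 10% loss and no clustering. The consequence is an unclear target and a precision claim attached to the wrong endpoint; neither a recruitment-stopping problem nor, on the NoLAP reading, an undersized study follows.

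**What to change.** Revise the Synopsis, the sample-size section and the Data analysis section as follows.

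- State that 700 counts NoLAP patients, once the sponsor has confirmed this.
- Reconcile the Synopsis, Outcomes and Data analysis sections on what is primary. Which quantity that should be is the sponsor's choice.
- Give the precision for NoLAP 90-day mortality: with 630 followed, about 3.1 to 3.9 points for assumed mortality of 20% to 80% (3.7 at 67%), described as before allowance for site clustering.
- Size the NoLAP share separately, on NoLAP plus ELAP patients at participating sites, without inflation for follow-up. Use about 2,188 if 32% is a share of all patients, or about 2,888 on the 8,000-to-25,000 ratio. Settle which use of 32% is meant first.
- If 590 is kept, write 656 at 10% loss, or state the 15.7% loss that 700 implies.

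The cost is protocol wording only; no additional patients or data collection are needed.
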